### **8.9. Severity Assessment**

If required on the AE CRFs, the investigator will use the adjectives MILD, MODERATE, or SEVERE to describe the maximum intensity of the AE. For purposes of consistency, these intensity grades are defined as follows:

MILD	Does not interfere with subject's usual function.
MODERATE	Interferes to some extent with subject's usual function.
SEVERE	Interferes significantly with subject's usual function.

Note the distinction between the severity and the seriousness of an AE. A severe event is not necessarily an SAE. For example, a headache may be severe (interferes significantly with the subject's usual function) but would not be classified as serious unless it met one of the criteria for SAEs, listed above.

### **8.10. Causality Assessment**

The investigator's assessment of causality must be provided for all AEs (serious and nonserious); the investigator must record the causal relationship in the CRF, as appropriate, and report such an assessment in accordance with the SAE reporting requirements if applicable. An investigator's causality assessment is the determination of whether there exists a reasonable possibility that the investigational product caused or contributed to an AE; generally the facts (evidence) or arguments to suggest a causal relationship should be provided. If the investigator does not know whether or not the investigational product caused the event, then the event will be handled as "related to investigational product" for reporting purposes, as defined by the sponsor (see section on [Reporting Requirements](#)). If the investigator's causality assessment is "unknown but not related to investigational product," this should be clearly documented on study records.

In addition, if the investigator determines that an SAE is associated with study procedures, the investigator must record this causal relationship in the source documents and CRF, as appropriate, and report such an assessment in accordance with the SAE reporting requirements, if applicable.

### **8.11. Exposure During Pregnancy**

For both unapproved/unlicensed products and for marketed products, an exposure during pregnancy occurs if:

1. A female becomes, or is found to be, pregnant either while receiving or having been exposed (eg, because of treatment or environmental exposure) to the investigational product; or the female becomes, or is found to be pregnant after discontinuing and/or being exposed to the investigational product;

An example of environmental exposure would be a case involving direct contact with a Pfizer product in a pregnant woman (eg, a nurse reports that she is pregnant and has been exposed to chemotherapeutic products).

2. A male has been exposed (eg, because of treatment or environmental exposure) to the investigational product prior to or around the time of conception and/or is exposed during his partner's pregnancy.

If a study subject or study subject's partner becomes or is found to be pregnant during the study subject's treatment with the investigational product, the investigator must submit this information to the Pfizer drug safety unit on a Serious Adverse Event (SAE) Report Form and Exposure During Pregnancy (EDP) supplemental form, regardless of whether an SAE has occurred. In addition, the investigator must submit information regarding environmental exposure to a Pfizer product in a pregnant woman (eg, a subject reports that she is pregnant and has been exposed to a cytotoxic product by inhalation or spillage) using the EDP supplemental form. This must be done irrespective of whether an AE has occurred and within 24 hours of awareness of the exposure. The information submitted should include the anticipated date of delivery (see below for information related to termination of pregnancy).

Follow-up is conducted to obtain general information on the pregnancy and its outcome for all EDP reports with an unknown outcome. The investigator will follow the pregnancy until completion (or until pregnancy termination) and notify Pfizer of the outcome as a follow-up to the initial EDP supplemental form. In the case of a live birth, the structural integrity of the neonate can be assessed at the time of birth. In the event of a termination, the reason(s) for termination should be specified and, if clinically possible, the structural integrity of the terminated fetus should be assessed by gross visual inspection (unless pre-procedure test findings are conclusive for a congenital anomaly and the findings are reported).

If the outcome of the pregnancy meets the criteria for an SAE (ie, ectopic pregnancy, spontaneous abortion, intrauterine fetal demise, neonatal death, or congenital anomaly [in a live-born baby, a terminated fetus, an intrauterine fetal demise, or a neonatal death]), the investigator should follow the procedures for reporting SAEs.

Additional information about pregnancy outcomes that are reported as SAEs follows:

- Spontaneous abortion includes miscarriage and missed abortion;
- Neonatal deaths that occur within 1 month of birth should be reported, without regard to causality, as SAEs. In addition, infant deaths after 1 month should be reported as SAEs when the investigator assesses the infant death as related or possibly related to exposure to the investigational product.

Additional information regarding the exposure during pregnancy may be requested by the investigator. Further follow-up of birth outcomes will be handled on a case-by-case basis (eg, follow-up on preterm infants to identify developmental delays). In the case of paternal exposure, the investigator will provide the study subject with the Pregnant Partner Release of Information Form to deliver to his partner. The investigator must document in the source documents that the subject was given the Pregnant Partner Release of Information Form to provide to his partner.

### **8.12. Occupational Exposure**

An occupational exposure occurs when during the performance of job duties, a person (whether a healthcare professional or otherwise) gets in unplanned direct contact with the product, which may or may not lead to the occurrence of an adverse event.

An occupational exposure is reported to the drug safety unit within 24 hours of the investigator's awareness, using the SAE report form, regardless of whether there is an associated AE/SAE. Since the information does not pertain to a subject enrolled in the study, the information is not reported on a Case Report Form (CRF), however a copy of the completed SAE report form is maintained in the investigator site file.

### **8.13. Withdrawal Due to Adverse Events (See Also the Section on [Subject Withdrawal](#))**

Withdrawal due to AEs should be distinguished from withdrawal due to other causes, according to the definition of AE noted earlier, and recorded on the appropriate AE CRF page.

When a subject withdraws because of an SAE, the SAE must be reported in accordance with the reporting requirements defined below.

#### **8.14. Eliciting Adverse Event Information**

The investigator is to report all directly observed AEs and all AEs spontaneously reported by the study subject and/or their parent/legally acceptable representative. In addition, each study subject and/or their parent/legally acceptable representative will be questioned about AEs.

#### **8.15. Reporting Requirements**

Each AE is to be assessed to determine if it meets the criteria for SAEs. If an SAE occurs, expedited reporting will follow local and international regulations, as appropriate.

##### **8.15.1. Serious Adverse Event Reporting Requirements**

If an SAE occurs, Pfizer is to be notified within 24 hours of investigator awareness of the event. In particular, if the SAE is fatal or life-threatening, notification to Pfizer must be made immediately, irrespective of the extent of available AE information. This time frame also applies to additional new information (follow-up) on previously forwarded SAE reports as well as to the initial and follow-up reporting of exposure during pregnancy, exposure via breastfeeding and occupational exposure cases.

In the rare event that the investigator does not become aware of the occurrence of an SAE immediately (eg, if an outpatient study subject initially seeks treatment elsewhere), the investigator is to report the event within 24 hours after learning of it and document the time of his or her first awareness of the AE.

For all SAEs, the investigator is obligated to pursue and provide information to Pfizer in accordance with the time frames for reporting specified above. In addition, an investigator may be requested by Pfizer to obtain specific additional follow-up information in an expedited fashion. This information collected for SAEs is more detailed than that captured on the AE CRF. In general, this will include a description of the AE in sufficient detail to allow for a complete medical assessment of the case and independent determination of possible causality. Information on other possible causes of the event, such as concomitant medications, vaccines, and/or illnesses, must be provided. In the case of a subject death, a summary of available autopsy findings must be submitted as soon as possible to Pfizer or its designated representative.

##### **8.15.2. Nonserious Adverse Event Reporting Requirements**

All AEs will be reported on the AE page(s) of the CRF. It should be noted that the form for collection of SAE information is not the same as the AE CRF. Where the same data are collected, the forms must be completed in a consistent manner. For example, the same AE term should be used on both forms. AEs should be reported using concise medical terminology on the CRFs as well as on the form for collection of SAE information.

### **8.15.3. Sponsor's Reporting Requirements to Regulatory Authorities**

AE reporting, including suspected unexpected serious adverse reactions, will be carried out in accordance with applicable local regulations.

## **9. DATA ANALYSIS/STATISTICAL METHODS**

Detailed methodology for summary and statistical analyses of the data collected in this study will be documented in a Statistical Analysis Plan, which will be maintained by the sponsor. This document may modify the plans outlined in the protocol; however, any major modifications of the primary endpoint definition and/or its analysis will also be reflected in a protocol amendment.

### **9.1. Sample Size Determination**

A sample size of approximately 170 subjects (in the polyarticular cohort) will be enrolled in the open-label active treatment run-in phase to provide a power of approximately 90% or above to detect a difference in the rate of disease flares between study drug versus placebo in the double-blind phase, assuming a 54% to 65% response rate of ACR Pedi 30 from the run-in active treatment phase, a 2-sided 5% Type I error, and a true difference of at least 31% in flare rates between tofacitinib and placebo, with a placebo flare rate of 57%. Sample sizes for the polyarticular JIA categories were determined from a combination of prevalence data and precedents in the literature.

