The cohort of subjects with polyarticular course JIA will have at least 170 subjects enrolled in the run-in phase with the minimum number of JIA categories as follows: 24 with extended oligoarthritis, 20 with polyarthritis RF+, and 62 with polyarthritis RF-. There is no minimum number of subjects with systemic JIA with active arthritis but without active systemic features. Additional cohorts (ie, psoriatic and enthesitis-related arthritis) will include a minimum of 20 subjects with psoriatic arthritis, and 20 subjects with enthesitis-related arthritis. The overall target minimum number of subjects to be enrolled in the study by age is as follows: 20 subjects 2 to <6 years, 20 subjects 6 to <12 years, and 20 subjects 12 to <18 years. The Sponsor will monitor enrollment and periodically notify investigator sites regarding the status of enrollment in the various JIA categories and age groups.

Initial screening and enrollment of subjects (at least the first 12 subjects) into Study A3921104 must be limited to 12 years of age or greater for all eligible JIA subtypes (rheumatoid factor negative [RF-] and positive [RF+] polyarthritis, extended oligoarticular, psoriatic arthritis, enthesitis related arthritis and systemic arthritis without systemic features JIA subtypes).

The duration of subject participation among those who complete the study (without discontinuation) is expected to be approximately 44 weeks. Pediatric blood tubes will be used (reduced volume) for testing to determine eligibility, monitor safety, and measure PK.

The study will be conducted over a period of approximately 3 years. CCI

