### **9.2. Efficacy Analysis**

#### **9.2.1. Analysis of Primary Endpoint**

Superiority of tofacitinib to placebo for the primary endpoint of percentage of subjects with disease flare at end of study Week 44 (Week 26 of the double-blind phase) for subjects with polyarticular course (polyarthritis RF+/RF-, extended oligoarthritis, and systemic JIA with active arthritis but without active systemic features) JIA will be tested using the normal approximation approach for the binomial populations. Subjects who discontinue from the study treatment for any reason will be considered as having a disease flare, except subjects who discontinue after maintaining JIA ACR inactive disease for at least 24 weeks in the double-blind phase. These discontinuations will be considered as non-disease flare.

Additional details of the analysis of the primary endpoint will be described in the Statistical Analysis Plan (SAP).

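### Does the stated power of approximately 90% or above fail at the low end of the 54% to 65% run-in response range?

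*Protocol*

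**What the plan says.** Protocol section 9.1 sets the size of the run-in: "A sample size of approximately 170 subjects (in the polyarticular cohort) will be enrolled in the open-label active treatment run-in phase". The aim is "to provide a power of approximately 90% or above to detect a difference in the rate of disease flares". On run-in response the text reads "assuming a 54% to 65% response rate of ACR Pedi 30 from the run-in active treatment phase". Testing is two-sided at the 5% level. The effect is put at "a true difference of at least 31% in flare rates between tofacitinib and placebo"; since 57% are taken to flare on placebo, the rate on tofacitinib is 26% at the minimum difference. Section 3 words the enrolment as a floor: "The cohort of subjects with polyarticular course JIA will have at least 170 subjects enrolled in the run-in phase". Randomisation is 1:1.

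The primary test in section 9.2.1 is a normal approximation for two binomial proportions. The same section settles the discontinuations: "Subjects who discontinue from the study treatment for any reason will be considered as having a disease flare". The one exception is for subjects who stop after at least 24 weeks of inactive disease in the double-blind phase. SAP section 5.2.1.1 repeats the normal approximation; its further detail is redacted, so the variance form cannot be seen. SAP section 4.1.1 analyses all polyarticular subjects who were randomised and dosed in the double-blind phase.

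**The concern.** Two things catch the eye.

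First, the claim covers a range of response rates and says 90% or above, yet at the bottom of that range only about 46 subjects per arm are randomised. With the pooled-variance formula that many statisticians use by default, power there is below 87%, and 90% is reached only at 60% response.

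Second, section 9.1 speaks of flare rates and mentions no discontinuations, while the primary endpoint scores nearly every discontinuation as a flare. If similar numbers stop in both arms for reasons other than flare, both rates rise and the difference between them shrinks.

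Section 9.1 is the justification shown for 170 children. If its power were clearly overstated, the trial could be too small for its purpose and a null result would be easy to misread.

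**Working it through.** **Inputs** (Protocol 9.1 and 3): N = 170 enrolled; response r = 54% to 65%; p_c = 0.57; p_t = 0.57 − 0.31 = 0.26; two-sided 5%, so z = 1.96; 1:1 allocation.

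**Numbers randomised.** 170 × 0.54 = 91.8, about 46 per arm. 170 × 0.65 = 110.5, about 55 per arm.

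**Reproducing the plan's figure, unpooled variance.** Power = Φ(0.31 / SE − 1.96), with SE = √[(0.57×0.43 + 0.26×0.74)/n] = √(0.4375/n).

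- n = 46: SE = 0.0975; 0.31/0.0975 = 3.18; Φ(1.22) = 88.9%.
- n = 55: SE = 0.0892; 0.31/0.0892 = 3.48; Φ(1.52) = 93.5%.

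**Pooled variance under the null.** Mean rate 0.415; SE₀ = √(2×0.415×0.585/n) = √(0.48555/n). Power = Φ[(0.31 − 1.96×SE₀)/SE].

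- n = 46: SE₀ = 0.1027; (0.31 − 0.2014)/0.0975 = 1.11; 86.7%.
- n = 55: SE₀ = 0.0940; (0.31 − 0.1842)/0.0892 = 1.41; 92.1%.

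**Exact binomial enumeration** of the same two tests:

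| Per arm | Unpooled formula | Pooled formula | Unpooled test, exact | Pooled test, exact |
|---|---|---|---|---|
| 46 (54%) | 88.9% | 86.7% | 87.2% | 86.0% |
| 55 (65%) | 93.5% | 92.1% | 92.7% | 91.8% |

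**How close 90% is.** The unpooled formula needs 48 per arm: 96/170 = 56.5% response. The pooled formula needs 51 per arm: 102/170 = 60%. At 46 per arm the shortfall is therefore two or five subjects per arm.

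**The minimums matter.** With a 32-point difference instead of 31, power at 46 per arm is 91.0% unpooled and 89.0% pooled.

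**Discontinuations.** Suppose, as an assumption, that 57% and 26% are flares by the criteria only, and that a fraction d of the non-flaring subjects in each arm stops treatment and is scored as a flare. Then p_c = 0.57 + 0.43d and p_t = 0.26 + 0.74d, and the difference is 0.31(1 − d).

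| d (assumed) | Rates | 46 per arm, unpooled / pooled | 55 per arm, unpooled / pooled |
|---|---|---|---|
| 5% | 59.1% vs 29.7% | 84.5% / 82.2% | 90.2% / 88.5% |
| 10% | 61.3% vs 33.4% | 79.7% / 77.3% | 86.3% / 84.4% |

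If instead 57% and 26% are rates of the endpoint as section 9.2.1 defines it, discontinuations are already inside them. The first table then applies unchanged. No inflation of the sample by 1/(1 − d) is due on either reading, because a subject who stops is counted as a flare and is not lost from the analysis.

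**The case for a change.** The best case against the plan is that exact enumeration is the real rejection probability. It gives 86.0% to 87.2% at 54% response, so the 88.9% flatters even the unpooled test. A continuity correction or Fisher's exact test would give about 81%. Stopping for reasons other than flare is certain to occur to some extent: the protocol requires it for serious infections and certain laboratory findings, and provides for it in persistent non-compliance. SAP section 3.1 also distinguishes flares derived by the coordinating centre from those assigned after discontinuation, so one could read 57% and 26% as the former alone.

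Part of this stands. No variant reaches a strict 90% at 54% response, and if the rates do exclude discontinuations, the loss in the second table is material. But section 9.1 claims approximate power, and nothing in the visible text points to a continuity correction or Fisher's test for the primary comparison. The reading that the rates exclude discontinuations is not documented. Section 9.2.1 makes discontinuations part of the flare endpoint, and SAP section 3.1 treats the assigned cases as a kind of disease flare. Reading the powered rates as rates of that endpoint is at least as natural. The 5% and 10% are illustrations and come from neither document.

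**Conclusion.** The concern does not hold. Under the protocol's own inputs, a standard unpooled normal approximation gives 88.9% to 93.5% over the 54% to 65% range, which reproduces a claim of approximately 90% or above. The pooled form gives 86.7% to 92.1%. At the low end the distance from 90% is 1 to 4 points across the pooled and unpooled formulas and their exact counterparts. Calling that a failure means choosing a variance formula that the visible documents do not name and holding a hedged statement to the exact figure, while both enrolment and effect size are given as minimums.

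The lower figures, 77% to 85% at 46 per arm with 5% to 10% discontinuation, depend on the assumption that the stated rates leave out discontinuations. The protocol does not say so. What remains is missing detail: section 9.1 does not state its variance formula, its power at 54% response, or what the 57% and 26% include. Supplying it would help a reader, but it would change no test, sample size or conclusion.

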### **9.2. Efficacy Analysis**

#### **9.2.1. Analysis of Primary Endpoint**

Superiority of tofacitinib to placebo for the primary endpoint of percentage of subjects with disease flare at end of study Week 44 (Week 26 of the double-blind phase) for subjects with polyarticular course (polyarthritis RF+/RF-, extended oligoarthritis, and systemic JIA with active arthritis but without active systemic features) JIA will be tested using the normal approximation approach for the binomial populations. Subjects who discontinue from the study treatment for any reason will be considered as having a disease flare, except subjects who discontinue after maintaining JIA ACR inactive disease for at least 24 weeks in the double-blind phase. These discontinuations will be considered as non-disease flare.

Additional details of the analysis of the primary endpoint will be described in the Statistical Analysis Plan (SAP).

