#### **7.1.7. PRCSG/PRINTO Disease Flare Criteria**

The PRCSG/PRINTO Disease Flare (Brunner 2002) determination is a derived measurement utilizing each component of the JIA core set variables (see [Section 7.1.6](#)).

Flare is defined as a worsening of 30% or more in 3 or more of the 6 variables of the JIA core set (see [Section 7.1.6](#)), with no more than one variable improving by 30% or more. In addition, the following minimum worsening contingencies apply: if either the number of active joints or the number of joints with limited range of motion are included in the calculation of "flare" then there must be a worsening of at least two joints. If the Physician's or parent/legal guardian/subject global rating scores are used in the definition of "flare" then there must be a worsening of at least 2 units on the 10 unit scales. If the ESR is used in the definition of "flare" then the second value for the ESR used in the calculation must be above the upper limit of normal for the ESR. For subjects with sJIA, presence of spiking fever due to sJIA will be considered sufficient to determine disease flare.

At each visit, the investigator will evaluate the subject for evidence of disease flare, according to PRCSG/PRINTO Disease Flare criteria, and confirmed by the Centralized Coordinating Center. Subjects who experience a single episode of disease flare (based on the investigator's and parent/legal guardian/subject's assessment of components of the JIA core set variables, and as confirmed by the Centralized Coordinating Center) will be discontinued from the study.

PRCSG/PRINTO disease flare will be based on the investigator and parent/legal guardian/subject assessment of components of the JIA core set variables, as confirmed by the Centralized Coordinating Center.

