### **3. ENDPOINTS AND BASELINE VARIABLES: DEFINITIONS AND CONVENTIONS**

#### **3.1. Primary Endpoint**

The primary endpoint of this study is:

- Occurrence of disease flare (according to PRCSG/PRINTO Disease Flare criteria) by Week 44/End of Study (Week 26 of the double-blind phase).

Only disease flare during the double-blind phase will be counted as primary endpoint.

Disease flare (except assigning as flare after discontinuation) will be derived by the Centralized Coordinating Center (CCC) using Erythrocyte Sedimentation Rate (ESR) in real-time, and double-blind baseline will be used to determine disease flare. CCI

[Redacted]

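### The readable primary flare test uses no covariate; a risk difference adjusted for Week 18 disease activity would need no new data and could add about 0 to 6 points of power, depending on an association the documents do not give

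*Protocol*

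**What the plan says.** Protocol 9.2.1 says that superiority on the flare percentage in polyarticular course JIA "will be tested using the normal approximation approach for the binomial populations". It leaves further detail to the SAP. SAP 5.2.1.1 repeats the method in one readable sentence; the rest of that section and the body of SAP 6.1 are redacted.

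The reference point for the endpoint is the state at randomisation: SAP 3.1 says "double-blind baseline will be used to determine disease flare". Protocol 7.1.7 gives the rule: "Flare is defined as a worsening of 30% or more in 3 or more of the 6 variables of the JIA core set". It adds minimum steps of two joints for the joint counts and two units for the global ratings, and ESR counts only if the later value is above the upper limit of normal.

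Randomisation in this cohort is stratified by JIA category and baseline CRP (Protocol 3). Protocol 7.1.5.1 says that this CRP is the Screening value, so it predates the run-in. The Week 18 core set is needed for the ACR 30 gate (Protocol 7.1.6). All four components of JADAS-27 ESR (Protocol 7.1.9) are scheduled at the Week 18 visit (Protocol 6.6).

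**The concern.** The flare rule makes the size of the worsening required depend on where the child starts.

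- **Joint counts.** The two-joint floor exceeds 30% below 2 / 0.30 = 6.7 joints. A child with 5 active joints needs 2 more for that variable to count; a child with 20 needs 6.
- **Global ratings.** These run from 0 to 10, so a score above 10 / 1.30 = 7.7 cannot worsen by 30% at all.

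Randomised children can start anywhere from a bare ACR 30 response to inactive disease. Week 18 disease activity is therefore a natural candidate predictor of flare, and stratification does not balance it. With roughly 46 to 55 children per arm, chance imbalance in such a predictor adds noise to an unadjusted difference. If Week 18 activity is prognostic, adjustment removes some of that noise. What is at stake is precision, not bias.

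**Working it through.** **Inputs (Protocol 9.1).** "A sample size of approximately 170 subjects (in the polyarticular cohort) will be enrolled"; "assuming a 54% to 65% response rate of ACR Pedi 30 from the run-in active treatment phase"; "a 2-sided 5% Type I error"; power, "to provide a power of approximately 90% or above"; "with a placebo flare rate of 57" per cent; true difference 31 points, so 26% on tofacitinib. Allocation is 1:1.

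**Step 1: the plan's own power.** Per arm, n = 170 × 0.54 / 2 = 45.9 to 170 × 0.65 / 2 = 55.25.

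- Unpooled: SE = √[(0.57×0.43 + 0.26×0.74)/n] = √(0.4375/n), and power = Φ(0.31/SE − 1.96). At n = 45.9, SE = 0.0976 and power is 88.8%. At n = 55.25, SE = 0.0890 and power is 93.6%.
- Pooled: SE₀ = √(2×0.415×0.585/n), and power = Φ[(0.31 − 1.96·SE₀)/SE], giving 86.7% and 92.2%.

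The stated power is broadly reproduced with no adjustment.

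**Step 2: what a prognostic covariate adds, by formula.** Replace n by n/(1 − R²) in the pooled version. R² is an assumption.

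| R² | Power, 54% randomised | Power, 65% randomised |
|---|---|---|
| 0 | 86.7% | 92.2% |
| 0.02 | 87.3% | 92.7% |
| 0.05 | 88.4% | 93.4% |
| 0.10 | 90.0% | 94.6% |
| 0.20 | 93.1% | 96.6% |

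**Step 3: simulation of the adjusted estimator.** Set-up: 46 per arm, marginal flare rates held at 57% and 26%, and one standardised Week 18 covariate acting linearly on the logit. The adjusted test is a logistic model standardised to a risk difference, with influence-function SE × √(N/(N−3)) and a t reference. There were 4,000 trials per row, so Monte Carlo error is about √(0.87×0.13/4000) = 0.5 points.

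| Assumed OR per SD | Unadjusted, pooled | Unadjusted, unpooled | Adjusted | Gain over pooled / unpooled | Variance ratio |
|---|---|---|---|---|---|
| 1.0 | 86.4% | 87.4% | 87.1% | +0.7 / −0.3 | 1.01 |
| 1.5 | 86.1% | 87.1% | 87.2% | +1.1 / +0.1 | 0.98 |
| 2 | 86.5% | 87.5% | 90.2% | +3.7 / +2.7 | 0.91 |
| 3 | 86.3% | 87.4% | 92.5% | +6.2 / +5.1 | 0.82 |

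About 1 point of any gain over the pooled test is only the difference between pooled and unpooled variance. At 55 per arm, with unpooled variances on both sides, the gains were about 0.7, 1.8 and 4 points for odds ratios 1.5, 2 and 3.

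**Step 4: type I error.** With 40% flare in both arms (8,000 trials), the corrected test rejected in 5.0 to 5.3% of trials and the uncorrected one in 5.7 to 6.0%. Across all settings examined, the uncorrected range was about 5 to 6.5%. The correction is needed.

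**Step 5: if the relation is not linear.** With a U-shaped effect, logit term 0.5(x² − 1), and a linear covariate fitted, power went from 86.9% to 87.7% at 46 per arm and stayed at 92.9% at 55.

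**Step 6: cost of the extra terms.** Week 18 activity (1), four JIA categories (3) and CRP (1) make five terms. At about 1% variance each, the worst case is 5% if none is informative. With n = 45.9/1.05 = 43.7, power would be 87.3% unpooled (from 88.8%) or 84.9% pooled (from 86.7%). Expected flares at the low end are 45.9 × (0.57 + 0.26) = 38, which is why sparse categories should be pooled.

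**The case against.** Three stronger readings are tempting, and the documents support none of them.

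- **That the plan ignores Week 18 state.** This can be said only of Protocol 9.2.1 and one SAP sentence. The redacted SAP text on binary methods and on the primary analysis may already adjust. The SAP contents list also shows sensitivity and supplementary analyses of the primary endpoint (6.1.2, 9.6.3) that cannot be read.
- **That power has been lost and must be recovered.** Step 1 roughly reaches the stated figure without adjustment. Under randomisation the unadjusted difference is valid, and its standard error already allows for chance imbalance.
- **That adjustment is free.** It needs an amendment line, a corrected standard error and a covariate form fixed in advance.

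The best counter-argument concerns the prognostic premise. No association between Week 18 state and flare is given. The flare rule pulls both ways: 30% is a small step from a low value, but the minimum steps block small changes. So even the direction is unknown. Counting discontinuation as flare may weaken any link. JADAS-27 ESR also leaves out two of the six flare components, the limited-motion joint count and the CHAQ Disability Index.

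All of this stands, and it is why the gain is given as a range starting at zero. It does not remove the case for adjusting. Pre-specified adjustment does not need the direction to be known, and the loss if the covariate is uninformative is small.

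**Conclusion.** The readable primary analysis is valid but unadjusted. It uses no information from the state against which flare is measured, although that information is collected for the randomisation decision and is not covered by the strata. Adjustment is worth pre-specifying as an efficiency measure; it does not correct an error.

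The gain is about 0 to 6 points of power at 46 to 55 per arm for assumed odds ratios of 1.0 to 3 per SD. It is negligible at 1.5 or below when variances are compared like for like at 46 per arm, and small if the relation is non-monotone. These figures rest on the planning rates in Protocol 9.1, on an assumed prognostic strength, and on simulations with a single covariate that is correctly modelled except in Step 5. The point falls away if the redacted SAP sections already contain such an analysis.

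**What to change.** First check the redacted parts of SAP 5.2.1 and 6.1. If they do not already adjust for Week 18 disease activity, specify the following before unblinding:

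- Keep the difference in flare proportions as the target. Estimate it by standardising, over the analysed polyarticular set, a logistic model with treatment, continuous Week 18 JADAS-27 ESR, JIA category and Screening CRP (normal, above normal). State in advance the rule for pooling sparse categories; Protocol 3 sets no minimum for systemic JIA.
- Use a robust or influence-function standard error with a small-sample correction that counts every model parameter, and a t reference. Confirm the type I error of the full model by simulation before fixing it, because the figures above are for one covariate.
- Report the unadjusted difference of proportions as a sensitivity analysis.

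The cost is one SAP paragraph, one extra model and one line in a protocol amendment, since Protocol 9 requires major changes to the primary analysis to appear there. No visit, sample or assessment is added.
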